13.5.5 PRO Analysis

13.5.5.1 EQ-5D-5L

Descriptive statistics, graphs and listings will be reported for health state utility values and visual analogue scale by visits as well as change in these scores from baseline. Further details will be included in the SAP.

13.5.5.2 FOSI-18

Descriptive statistics, graphs and listings will be reported to explore the impact of NUC-1031 on symptoms and HRQoL. The relationship between PROs, efficacy and AEs will be explored using descriptive summaries. Further details of the exploratory analysis based on the FOSI-18 will be outlined in the SAP.

13.5.6 Safety Analysis

Safety analyses in addition to those described in the following subsections may be determined at any time without prejudice, in order to most clearly enumerate rates of toxicities and to define further the safety profile of NUC-1031.

13.5.6.1 Adverse Events

AEs will be considered treatment-emergent (TEAE) if they start on or after the time of the first dose of study treatment and up to 30 days after the last dose of study treatment. AEs will be summarized by MedDRA™, Version 18.1 (or higher), System Organ Class (SOC) and preferred term (PT). The severity of AEs will also be summarized by NCI CTCAE v4.03 (or higher), grade. Non-treatment-emergent AEs will be included in the patient listings and flagged as such but will not be included in the summary tables. Where an AE date is partial or missing, and it is unclear whether the AE is treatment-emergent, the AE will be assumed to be treatment-emergent.

The following summaries will be produced by dose cohort for all TEAEs:

- An overview table of the incidence of TEAEs, Grade 3+ TEAEs, SAEs, TEAEs leading to treatment discontinuation and TEAEs leading to death, by dose and overall.
- Summary of TEAEs by SOC and preferred term: Both the number and percentage of patients in each category (patient-level summary) and the number of episodes (episode-level summary).
- Summary of TEAEs occurring in at least 10% of patients, sorted in descending order of frequency (*i.e.* most frequent event shown first). The order of frequency will be determined by the most frequent preferred term across all cohorts.
- Summary of CTCAE Grade 3 and above TEAEs by preferred term.
- Summary of SAEs by preferred term.

In addition, the following will be listed:

- AEs with outcome of death along with the date of onset, study day, dose at onset, treatment status at onset (pre-treatment, ongoing or post-treatment) and investigator's assessment of severity and relationship to study drug.
- All SAEs along with the date of onset, study day, dose at onset, treatment status at onset (pre-treatment, ongoing or post-treatment), date of resolution (if AE is resolved), investigator's assessment of severity and relationship to study drug.
- AEs leading to discontinuation of study medication, listed along with the date of onset, study day, dose at onset, treatment status at onset (pre-treatment, ongoing or post-treatment) and investigator's assessment of severity and relationship to study drug.
- If an AE is reported more than once during the study period the greatest severity and the worst-case attribution will be presented in summary tables. Any AEs commencing >30 days after discontinuation of study treatment will not be included in the tabulations of AE data.

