5.2 Patient Registration and Screening Procedures

All screening activities must be performed within 28 days of randomization. A Screening Log must be kept of all patients considered for the study (*i.e.* all those that are included for screening and any that are subsequently excluded). The reason for exclusion must be recorded on this form. A copy of the Screening Log must be retained on site and provided to the CRO upon request, but without patient identifiers.

In Part I, patient randomization will be stratified according to BRCA mutation status and number of prior lines of chemotherapy (3 or ≥ 3). In Part II, sensitivity analyses will be conducted of efficacy endpoints according to BRCA mutation status. Patients known to have germline BRCA mutation(s) prior to randomization can enter the study based on this result. Patients who have had a tumor BRCA mutation identified in a certified laboratory may also be enrolled on the study based on this result. Patients with unknown BRCA mutation status should undergo local BRCA mutation testing prior to study entry, according to local ethical procedures for genetic testing.

Before entering a patient onto the study, the Medical Monitor, in consultation with the Sponsor, will confirm eligibility according to the defined inclusion and exclusion criteria. Details of the query and outcome of the decision must be documented on the registration/ eligibility checklist. To register a patient to the study, the site must email a completed Registration Form, along with a copy of the blinded histology report, to the patient registration email address supplied. The site will be informed by email and fax of the approval to be treated. Treatment must not start until this registration process is complete and must start no later than 10 days after the day of registration.

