12 SAFETY REPORTING

12.1 Definitions

The Investigator is responsible for reporting all AEs that are observed or reported during the study, regardless of their relationship to study drug or their clinical significance.

An **AE** is defined as any untoward medical occurrence in a patient enrolled into this study regardless of its causal relationship to study drug. Patients or their legally authorized representatives will be instructed to contact the Investigator or Sub-Investigator at any time after signing the ICF if any symptoms develop.

A Treatment Emergent AE (**TEAE**) is defined as any event not present before exposure to study drug or any event already present that worsens in either intensity or frequency after exposure to study drug.

A Serious AE (**SAE**) is defined as any event that:

- Results in death,
- Is immediately life-threatening,
- Requires inpatient hospitalization or prolongation of existing hospitalization,
- Results in persistent or significant disability/incapacity,
- Is a congenital anomaly/birth defect,
- Significant medical event in the investigator's judgment (*e.g.*, may jeopardize the patient or may require medical/surgical intervention to prevent one of the outcomes listed above)

PD and disease-related death will not be considered an AE or SAE.

An **Adverse Drug Reaction (ADR)** is an AE, which is considered to be causally related to any dose of NUC-1031. This means that a causal relationship between NUC-1031 and the AE is at least a reasonable possibility, *i.e.* the relationship cannot be ruled out.

An **Unexpected Drug Reaction** is an adverse drug reaction, the nature or severity of which, is not consistent with applicable product information (referring to information in IB, see RSI).

A **Suspected Unexpected Serious Adverse Reaction (SUSAR)** is a serious adverse drug reaction, the nature or severity of which is not consistent with the applicable product information (*e.g.* Investigator's Brochure for an unapproved IMP).

Important medical events that may not result in death, be life threatening, or require hospitalization may be considered an SAE when, based upon appropriate medical judgment, they may jeopardize the patient and may require medical or surgical intervention to prevent one of the outcomes listed in this definition. Examples of such medical events include allergic bronchospasm requiring intensive treatment in an emergency room or at home, blood

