12.2 Adverse Event Reporting

At every study visit, patients will be asked nondirective questions to elicit any medically related changes in their well-being. They will also be asked if they have been hospitalized, had any accidents, used any new medications, or changed concomitant medication regimens (both prescription and over-the-counter medications). In addition to patient observations, AEs will be documented from any data collected on the CRF or other documents that are relevant to patient safety. Any allergic reaction to the agents administered as study drug treatment must be reported as an AE.

All AEs that occur from date of consent through 30 days after the last dose of study drug must be reported in detail on the AE CRF. Disease progression in the medical opinion of the physician and/or disease-related morbidity and mortality as a study endpoint will not be considered an AE or SAE but should be captured on the Death CRF. Information to be collected for each AE includes onset date, type of event, etiology, Investigator-specified assessment of severity and relationship to study drug, seriousness, any required treatment or evaluations, outcome and date of resolution. AEs resulting from concurrent illnesses, reactions to concurrent illnesses, reactions to concurrent medications, or progression of disease states must also be reported. All AEs will be followed for 30 days after the patient's last dose, or until resolution, whichever comes first.

Pre-existing conditions (present before the start of the AE collection period) are considered concurrent medical conditions and should not be recorded as AEs. However, if the patient experiences a worsening or complication of such a concurrent condition, the worsening or complication should be recorded as an AE. Pre-existing AEs that worsen should be followed until 30 days after the patient's last dose or resolution to the AE level present at study entry. Investigators should ensure that the AE term recorded captures the change in the condition (*e.g.* "worsening of [condition]").

Insufficient clinical response, efficacy, or pharmacological action should NOT be recorded as an AE. The Investigator must make the distinction between exacerbation of pre-existing illness and lack of therapeutic efficacy. PD is NOT an AE; however, some sequelae of PD (*i.e.* pain, neurologic impairment) may be reported as AEs (generally not related to NUC-1031).

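### Sections 12.1 and 13.5.6.1 define a treatment-emergent AE differently, so an AE that starts between consent and first dose and worsens on drug can be missing from the TEAE tables

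*Protocol*

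**What the plan says.** Protocol section 12.1 (Definitions) has two limbs. The first covers new events: "any event not present before exposure to study drug". The second extends the term to existing ones: "any event already present that worsens in either intensity or frequency after exposure to study drug". It sets no end to the period in which such an event counts.

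Protocol section 13.5.6.1 (Adverse Events), which governs the tables, has one limb. AEs are treatment-emergent "if they start on or after the time of the first dose of study treatment"; the period closes 30 days after dosing ends. Worsening is not mentioned. The consequence of falling outside the rule is explicit: "Non-treatment-emergent AEs will be included in the patient listings and flagged as such but will not be included in the summary tables".

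Section 12.2 (Adverse Event Reporting) starts collection before treatment: "All AEs that occur from date of consent through 30 days after the last dose of study drug" must be reported. It then treats two situations separately:

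- A condition present before AE collection begins is not an AE, but its worsening is to be recorded as one.
- An AE that already exists and worsens is to be followed, for a stated period or until it returns to its level at study entry.

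A further sentence asks that the recorded term should reflect the change in the condition.

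**The concern.** Both definitions are current text of the same protocol, and they do not select the same events. Anyone programming the tables has to choose one. A site that classifies by 12.1 and a programmer who applies 13.5.6.1 can reach different answers for the same event.

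TEAEs are a secondary safety endpoint (section 2.5), and safety is one of the inputs to the choice of dose for Part II (sections 3.1 and 12.13). A symptom that was Grade 1 before the first infusion and became Grade 3 on drug is what a worsening limb is meant to catch. The analysis rule has no such limb.

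**Working it through.** No arithmetic underlies this point and the protocol gives no figure to reproduce. The check sets the two definitions against each kind of event that the recording rules can produce.

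**Can an AE start before first dose?** Yes. Collection runs from consent (12.2), and note 1 to the Summary Schedule of Events has changes from consent onwards recorded as AEs. Section 5.2 says "All screening activities must be performed within 28 days of randomization", and that treatment "must start no later than 10 days after the day of registration". Added together these give 28 + 10 = 38 days. That is an upper bound, because registration is itself listed among the screening activities (section 5.3). Screening also includes a fresh biopsy where tumor is easily accessible, so procedure-related AEs before dosing are plausible.

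**Classification by case**

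1. *New event from first dose to 30 days after last dose.* TEAE under both sections.
2. *Condition present before consent that worsens on drug.* TEAE under 12.1. Also a TEAE under 13.5.6.1 if the site follows 12.2, records the worsening as its own AE and dates it from the worsening.
3. *AE that starts between consent and first dose and worsens on drug.* TEAE under 12.1. Not a TEAE under 13.5.6.1, because its onset precedes "if they start on or after the time of the first dose of study treatment", unless the site opens a new record with a new start date.
4. *New event starting more than 30 days after last dose.* TEAE under the wording of 12.1, which has no upper limit. Not a TEAE under 13.5.6.1.

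The sections diverge in cases 3 and 4, and in case 2 if the start date is not reset.

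**Does any other text close case 3?**

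- The instruction in 12.2 to record worsening as an AE is tied to conditions that predate AE collection. For AEs already under collection it specifies follow-up.
- The sentence in 12.2 about the recorded term can be read as reaching such AEs, but it governs the term and requires neither a new record nor a new start date.
- The items that 12.2 lists for each AE include onset and resolution dates but no date of grade change. If the event stays one record, its pre-dose onset decides its status.
- The rule in 13.5.6.1 that resolves doubt in favour of treatment-emergent applies to partial or missing dates. Here the onset is known.
- Section 13.5.6 allows additional safety analyses but does not require one for this.

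**Direction.** In case 3 the start-date rule removes events that 12.1 would count and adds none. It can lower tabulated TEAE and Grade 3+ incidence but cannot raise it.

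**The case against.** The strongest reply is that the protocol already captures most of what matters.

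- **Recording.** Section 12.2 and schedule note 1, read together, point sites towards recording a worsening as an AE, and a record made that way would normally carry an on-treatment start date. This stands for conditions that predate consent. For AEs that begin after consent it depends on site practice, because no text requires a new start date. The AE form and its completion guidelines are not in the protocol and may already handle this.
- **Visibility.** Non-treatment-emergent AEs stay in the listings and are flagged. SAEs, fatal AEs and AEs leading to discontinuation are listed with pre-treatment onset as an explicit category. Laboratory worsening appears in the CTCAE shift tables (13.5.6.2), and laboratory abnormalities were the most common treatment-related events in the earlier single-agent study (section 1.4.2). This also stands. What remains is mainly symptomatic, non-serious worsening, which is listed but not tabulated.

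A reader might also infer more than the text supports:

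- *That TEAE rates are biased low for heavily pre-treated patients with baseline symptoms.* Those symptoms mostly predate consent, and 12.2 has their worsening recorded as an AE.
- *That the gap drives dose selection.* Safety stands beside dosing intensity, PK and clinical activity, and no TEAE threshold is stated.
- *That the effect is 5 percentage points.* One patient in a full Part I arm is 1/20 = 5 points, and one in 44 is 1/44 = 2.3 points, but this holds for any event. It does not show that a single patient is affected. A patient already counted under the same term and grade changes nothing, and in the earlier study every patient had at least one TEAE, so overall incidence may have no room to move.

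**Conclusion.** The contradiction is real and the analysis rule, as written, can give a wrong count. An AE that starts between consent and first dose and worsens on drug is a TEAE under 12.1 but is absent from the TEAE and Grade 3+ tables under 13.5.6.1, unless the site re-enters it with a new start date. The missing upper time limit in 12.1 is a second, lesser mismatch.

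The effect runs one way, towards lower tabulated incidence. Its size cannot be stated, because the protocol gives no count of such events. It is likely small, since the affected window is short, pre-consent conditions are largely covered, and some of these events remain visible elsewhere.

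The conclusion assumes that sites may extend the existing AE record when an event worsens, which 12.2 does not forbid. If the CRF instructions already require a new dated record, the case 3 counting gap closes and only the wording needs to be harmonised. The point should be corrected, but it does not undermine the trial's safety evaluation.

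**What to change.** Use one definition in both sections: an AE that starts, or worsens in intensity (CTCAE grade) or frequency, on or after first dose and up to 30 days after last dose.

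- **13.5.6.1:** add the worsening limb. Grade alone would not match 12.1, which also names frequency.
- **12.1:** add the 30-day upper limit, so that the definitions agree at both ends.
- **12.2:** state that worsening after first dose of any AE, including one that began after consent, is entered either as a new record with its own start date or as a dated grade change on the existing record.

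The cost is wording in three places and a CRF completion instruction or one added field. Tabulated TEAE rates may rise slightly.

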- 17.** For women of child-bearing potential, serum pregnancy testing must be performed within 72 hours prior to C1D1 and at End of Treatment visit. In addition, urine pregnancy tests will be performed pre-dose on Day 1 of each cycle. If any urine test result is positive, patient dosing will be postponed until the result is confirmed by a serum pregnancy test. Patients with a positive serum test will be discontinued from the study.
- 18.** Includes insertion of central venous access device, if not already present (if NUC-1031 is centrally administered).
- 19.** Optional fresh biopsy tissue sample collection within 24 hours post administration of C1D1 dose for patients who consent.
- 20.** Includes treatment discontinuation due to disease progression or early treatment discontinuation for other reasons (*e.g.* withdrawal of consent). Progressive disease should be confirmed prior to stopping treatment. Visit to occur within 30 (± 7) days of the last dose of NUC-1031.
- 21.** Patients withdrawing from the study with no radiological evidence of disease progression will receive scans every 8 weeks (± 7 days) from C1D1 until disease progression, initiation of a new treatment or death in order to determine duration of overall response and PFS.
- 22.** Adverse events should be captured from the time of consent up to 30 days after the last dose of NUC-1031. SAEs deemed definitely, probably or possibly related to NUC-1031 but outside of this window (>30 days from last dose of NUC-1031) should also be captured in the eCRF.
- 23.** Patients with evidence of disease progression as defined by RECIST criteria will receive a phone call at regular intervals (every 12 weeks ± 7 days) until death, loss to follow-up, or study discontinuation in order to determine duration of Overall Survival.

ABBREVIATIONS

°C	Degrees Centigrade
AE	Adverse event
ALT	Alanine aminotransferase
ANC	Absolute neutrophil count
AST	Aspartate aminotransferase
AUC	Area under the curve
AUC _{0-t}	Area under the plasma concentration-time curve from time zero to the last measurable concentration
BICR	Blinded Independent Central Reviewer
BRCA 1/2	Breast cancer (gene) 1/2
BUN	Blood urea nitrogen
CA125	Cancer Antigen 125
CDA	Cytidine deaminase
CL	Apparent clearance
C _{max}	Maximum plasma concentration; peak plasma concentration
CNS	Central Nervous System
CR	Complete Response
CRF	Case report form
CRO	Clinical Research Organization
CSR	Clinical study report
CT	Computed tomography

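### Late drug-related SAEs are to be captured but enter no AE summary table, and the protocol's own rules disagree on whether they are treatment-emergent

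*Protocol*

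**What the plan says.** **Collection.** Note 22 to the Summary Schedule of Events sets an AE window from consent to 30 days after the last dose. It then adds that SAEs judged at least possibly due to the drug and falling "outside of this window (>30 days from last dose of NUC-1031) should also be captured in the eCRF". No end date is given for this extension. Sections 12.2 and 12.5 do not repeat it: 12.2 requires AE reporting from consent, and 12.5 SAE reporting from first dose, each to 30 days after the last dose.

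**Definition.** Section 12.1 calls an event treatment-emergent if it was absent before exposure, or was present and worsened after exposure. It sets no upper time limit. Section 13.5.6.1 limits treatment-emergence to events starting from the first dose "up to 30 days after the last dose of study treatment".

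**Tables.** Section 13.5.6.1 introduces its summaries with "The following summaries will be produced by dose cohort for all TEAEs". The list under that sentence includes the overview table (with SAE and death rows), the Grade 3 and above table and the SAE table. Two further rules apply: "Non-treatment-emergent AEs will be included in the patient listings and flagged as such but will not be included in the summary tables", and "Any AEs commencing >30 days after discontinuation of study treatment will not be included in the tabulations of AE data". Neither makes an exception for related SAEs.

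**Listings.** The same section lists fatal AEs and "All SAEs along with the date of onset, study day, dose at onset, treatment status at onset (pre-treatment, ongoing or post-treatment"), with severity and the investigator's view of relationship.

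**The concern.** The late events that note 22 singles out are those judged both serious and related to the drug. Under the stated rules they contribute nothing to any tabulated incidence: not to the SAE row, the Grade 3 and above row or the death row. If any occur, the understatement runs in one direction only, because omission can lower these figures but never raise them.

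TEAEs are a named safety endpoint in section 2.5. Two definitions of a TEAE in one protocol mean that the endpoint has two possible values on the same data. Sites also face two instructions on late related SAEs: a schedule footnote that asks for them and a reporting section that stops at 30 days. That makes it uncertain how completely they will be collected.

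**Working it through.** No stated figure is in dispute, so the check consists of putting one record through each rule.

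**Hypothetical record.** The last dose is on Day 15 of Cycle 3. With 28-day cycles (section 3.3) that is study day 2 × 28 + 15 = 71. A related fatal SAE starts on Day 105, which is 105 − 71 = 34 days after the last dose.

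| Rule | Result for this record |
|---|---|
| Note 22 | Should be captured in the eCRF |
| 12.5 | Outside the SAE reporting window |
| 12.1 | Is a TEAE |
| 13.5.6.1, TEAE window | Is not a TEAE (34 > 30) |
| 13.5.6.1, overview, Grade 3+ and SAE tables | Adds 0 to each |
| 13.5.6.1, listings | Appears, with post-treatment status |

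**Size per affected patient.**
- Full Part I cohort of up to 20 (section 3.1): 1/20 = 5.0 percentage points.
- Selected dose: the Safety Analysis Set is all patients given at least one dose (section 13.3). Section 4.4 speaks of 44 response-evaluable patients treated at that dose, so the safety denominator is 44 or more. The size is at most 1/44 = 2.3 points.
- Overall column, at the planned maximum of 64 patients (section 3.1): 1/64 = 1.6 points.

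These are sizes per patient, not expected effects. The protocol gives no rate for such events.

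**The two 30-day anchors.** One limit in 13.5.6.1 runs from the last dose and the other from discontinuation, for which the protocol fixes no date. Suppose discontinuation is dated when re-treatment is finally refused. The last dose is then Day 15, the next cycle is due on Day 29, and the 14-day delay allowed in section 9 gives Day 43. The anchors differ by 43 − 15 = 28 days, and the second limit falls 28 + 30 = 58 days after the last dose. If discontinuation is dated at the last dose, the gap is 0.

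An event 31 to 58 days after the last dose is thus not excluded by the second rule under the first dating. It is still not a TEAE, and the tables hold TEAEs only. The second rule can only exclude, so the table count is the same under either dating.

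**The case against.** The strongest reply is that this is an ordinary design: a fixed 30-day window for the tables, with everything outside it listed and flagged. The plan collects more than it tabulates elsewhere too, since AEs between consent and first dose are recorded but not summarised. Collecting late events and only listing them is therefore no contradiction in itself, and that part of the reply stands.

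Several stronger readings are tempting, but the text does not support them.

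- *The late events are lost.* They are not. All SAEs and all fatal AEs are listed with onset date, severity and relationship, and section 13.5.6 allows further safety analyses. But a listing gives no incidence, and those further analyses are optional.
- *Capture is mandatory.* Note 22 says should, not must.
- *The safety endpoint is shown to be biased.* Nothing in the protocol indicates that such events will occur or how often. Under 13.5.6.1 they fall outside the endpoint by definition. The difficulty is that 12.1 defines the endpoint differently.
- *The two anchors change the results.* They do not, because the last-dose rule governs every table.
- *Related SAEs should count as TEAEs whenever they start.* This would mix a systematically observed window with open-ended follow-up. The schedule marks AE collection at the 8-weekly follow-up visits for patients without progression, but not at the 12-weekly survival calls after progression (section 5.5.8). Ascertainment of late events will be uneven, and a pooled rate would have no defined time at risk.

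What remains is the conflict between 12.1 and 13.5.6.1, the silence of 12.5 on note 22, and the lack of any tabulated count of late related SAEs.

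**Conclusion.** The point holds as a minor one. An SAE related to NUC-1031 that starts more than 30 days after the last dose should be captured under note 22, is a TEAE under 12.1, lies outside the reporting window of 12.5, and is barred from every summary table by 13.5.6.1. Each such patient leaves the tabulated SAE incidence low by 5.0 points in a full Part I cohort and by at most 2.3 points at the selected dose. The same applies to the death row if the event is fatal.

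These sizes assume that the patient has no other SAE inside the window; otherwise she is already counted in the SAE row. They also assume a Part I cohort of 20 and at least 44 treated patients at the selected dose. The number of such patients is unknown and may be zero. The 30-day window is acceptable, and the difference in anchor wording is editorial.

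**What to change.** 1. Keep the TEAE window at 30 days from the last dose for the main tables.
2. Give section 12.1 the same upper limit as 13.5.6.1, or have it refer to that section.
3. Make section 12.5 and note 22 agree on related SAEs starting more than 30 days after the last dose, so that sites have one instruction.
4. Add to the overview and SAE tables a separate row for related SAEs, and for related fatal events, starting more than 30 days after the last dose. Report number and percentage of the Safety Analysis Set, by dose. A footnote should say that follow-up for these events is less complete than inside the window.
5. As tidying only, anchor the closing exclusion in 13.5.6.1 to the last dose, with an exception for the new row.

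The cost is a few sentences, slightly more programming and no new assessments, since note 22 already asks for the data. The reported SAE and death figures may look slightly less favourable. Late events will be incompletely ascertained, but a separate row shows this openly and leaves the main rates unchanged.
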